We are proposing broad inclusion criteria that reflect the heterogeneity of individuals seeking treatment for alcohol use disorders in this setting. Literacy is not required for using the CBT4CBT program, and, as described below, most of the assessment instruments we use are clinical interviews or can be administered by reading the questions to the participants using procedures we have worked out in our ongoing and previous trials¹⁹³⁻¹⁹⁷. We are not requiring that participants have computer access for study inclusion, as participants can access the program at the clinic.

3. Procedures

a. Initial Screening

All new admissions will be invited to participate in the protocol within two weeks of their clinic appointment. They will be identified by their clinicians at CMHC, the Hispanic Clinic, SATU for MAAS, interest sheets, and clinic postings. Individuals who indicate they are interested in hearing more about the study will be offered a meeting with the research staff. An interest sheet providing a brief description of the study will be available for potential subjects to indicate their interest in learning more about the study and how to contact a member of the research team, should they be unable to speak with the research staff at the time of the clinic intake appointment. At the first interview, research staff will provide a brief overview of the protocol and obtain written informed consent. We use a multiple-choice test to assess participants' comprehension of the protocol^{122, 137}, with ample time to review questions to assure understanding of the protocol, consent, and treatments offered. After determination of eligibility, pretreatment assessments will be completed by the research assistant (see Table below).

b. Urn randomization

To prevent bias and increase the likelihood that treatment groups are balanced with respect to demographic variables (*gender, education*) and possible prognostic variables (severity of alcohol use, level of familiarity with and access to computers, level of acculturation) participants will be assigned to treatment conditions through urn randomization, using a Microsoft Access program that we have developed and implemented successfully in multiple previous trials¹⁹⁸⁻²⁰². In urn randomization, an algorithm modifies ongoing randomization probabilities based on prior

composition of treatment groups, maximizing multivariate equivalence of treatment groups²⁰³, while still retaining other benefits of random assignment²⁰⁴.

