c. *Evaluation of treatment effects at posttreatment and follow-up*: The principal strategy for assessing the efficacy of the study treatments on outcome over time will be random effects regression models for continuously measured primary (e.g. percent days of abstinence by week) and secondary (e.g., acquisition of coping skills) outcome variables. The focus of the repeated measures analyses will be the 'contrast by time effects', which essentially evaluates whether the slopes, or rates of change, of one group differ from the slopes of another group. We have used these methods to evaluate main and interaction effects, with appropriate covariates (e.g., retention, compliance with treatment, time spent working with the CBT4CBT program) in multiple previous trials^{14, 151, 160, 200, 201, 254}. Follow-up data will be analyzed using random-effects regression modeling²⁵⁵ for our primary outcome measures across time, using the contrasts described above, with appropriate covariates (e.g., length of time in treatment, exposure to other treatment during follow-up). Random effects regression models have several advantages in follow-up data from clinical trials of substance users where participants are unlikely to attend follow-up evaluations precisely at the desired fixed points, and are less vulnerable than traditional MANOVA approaches to missing data^{208, 209, 251, 252}. As in our previous trials^{16, 126}, we estimate that our extensive efforts to track participants will yield a 90% follow-up rate.

d. *Adequacy of sample size*: This Stage 1 trial is intended to provide initial pilot testing and feasibility testing of the web-based CBT4CBT program in a Spanish-speaking sample of individuals with alcohol use disorder. Based on SSize software, the proposed sample sizes will enable us to detect effect sizes of .35 or higher for either hypothesis, which will be the criterion for determining whether CBT4CBT-Spanish-Alcohol has adequate promise to justify a fully powered randomized trial²⁵⁶. This sample size was sufficient for the English-language trials of the drug and alcohol versions of CBT4CBT, which yielded effect sizes of .46-.59^{13, 15, 16}.

Power calculations for random effects regression	Power	Estimated effect size	Estimated ICC	# of datapoints	Sample size per cell
H1: (CBt4CBT-S + ST) v ST, main effect for active treatment phase (assessed weekly, baseline-8weeks)	.80	.35	.40	9	45

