H2: (CBT4CBT-S + ST) vs ST, main effect for follow-up (assessed monthly, end of treatment-6 months)	.80	.50	.80	7	40

2. Treatment specificity and mediators

We will explore the extent to which participants improve coping skills over time using the ARRT as described above and the extent to which acquisition of coping skills may mediate outcome for CBT4CBT-Spanish-Alcohol in this sample. We have described our use of these models and strategies to evaluate treatment mediators in Preliminary Studies, above, and in several papers^{13, 105, 108, 151}. Following the general analytic framework outlined by Kraemer²⁵⁷, we will use the product of the coefficients method to evaluate the relationship between the mediator (e.g., acquisition of CBT-specific coping skills as measured by the ARRT), or indirect effect, and outcome^{155, 156, 258}. After running a regression equation to determine (1) the effect of treatment on the mediator (provides beta weight for a), we will evaluate (2) the strength of the relationship between the mediator, treatment, and outcome (provides beta b). Using MacKinnon's software PRODCLIN²⁵⁹, we will evaluate the asymmetric confidence intervals for the product of the regression estimates (a^*b).

SECTION VI: RESEARCH INVOLVING DRUGS, BIOLOGICS, PLACEBOS AND DEVICES

If this section (or one of its parts, A or B) is not applicable, state N/A and delete the rest of the section.

N/A

SECTION VII: HUMAN SUBJECTS

1. Subject Population:

Provide a detailed description of the types of human subjects who will be recruited into this study.

Participants will be individuals seeking outpatient treatment for alcohol use at the Connecticut Mental Health Center (CMHC), where the majority of clients are male (73%), middle aged (62%), unemployed (71%), unmarried (56%), and have not completed high school (64%). Spanish-speaking participants will be recruited from two CMHC outpatient programs (The Hispanic Clinic at [name] and the Substance Abuse Treatment Unit at [name]) or Connecticut Mental Health Center clinicians. Additionally, MAAS (The Multi- Cultural Ambulatory Addiction Service at [name]) has been appointed a recruitment site

2. Subject classification:

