### **1. Determination of Treatment Outcomes**

*a. Data reduction:* Primary outcome variables have been defined *a priori* to reduce the risk of Type I error. Preparatory analyses include evaluation of baseline equivalence of treatment groups on demographic and prognostic variables and comparability of rates of data availability across conditions.

*b. Strategies for management of differential attrition:* Data analyses will be conducted on the intent-to-treat sample and we will attempt to follow all participants regardless of their retention in treatment. We have established our ability to contact and follow participants who drop out of treatment and to conduct true intent-to-treat analyses, including supplemental analyses that account for whether data was collected before or after dropout/withdrawal. While we anticipate that assertive efforts to locate and interview participants who drop out of treatment will result in low numbers of missing participants and minimal missing data in the final dataset, we will minimize the impact of missing data through the use of random effects regression modelling.

*c. Evaluation of treatment effects at posttreatment and follow-up:* The principal strategy for assessing the efficacy of the study treatments on outcome over time will be random effects regression models for continuously measured primary (e.g. percent days of abstinence by week) and secondary (e.g., acquisition of coping skills) outcome variables. The focus of the repeated measures analyses will be the 'contrast by time effects', which essentially evaluates whether the slopes, or rates of change, of one group differ from the slopes of another group. We have used these methods to evaluate main and interaction effects, with appropriate covariates (e.g., retention, compliance with treatment, time spent working with the CBT4CBT program) in multiple previous trials. Follow-up data will be analyzed using random-effects regression modeling for our primary outcome measures across time, using the contrasts described above, with appropriate covariates (e.g., length of time in treatment, exposure to other treatment during follow-up). Random effects regression models have several advantages in

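### The analysis text does not specify adjustment for pre-treatment PDA or the urn variables, which forgoes precision for the average contrasts and the follow-up model

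*Protocol*

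**What the plan says.** Protocol Section V.3, B.3.b (Urn randomization) balances allocation on gender, education and "possible prognostic variables (severity of alcohol use, level of familiarity with and access to computers, level of acculturation", with the aim of "maximizing multivariate equivalence of treatment groups".

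The analysis text (Protocol Section V.5, 1.a-1.d; SAP 1.a-1.c) mentions covariates twice:

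- For the treatment phase: "We have used these methods to evaluate main and interaction effects, with appropriate covariates (e.g., retention, compliance with treatment", followed by time on the program. This sentence describes previous trials.
- For follow-up in this trial: "with appropriate covariates (e.g., length of time in treatment, exposure to other treatment during follow-up".

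All five examples arise after randomisation. The only use of baseline variables stated in the SAP is a check: "Preparatory analyses include evaluation of baseline equivalence of treatment groups on demographic and prognostic variables". No consequence of that check is given. The Protocol's Assessments section also lists gender and acculturation as exploratory moderators.

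On the estimand, SAP 1.c says "The focus of the repeated measures analyses will be the 'contrast by time effects", that is, a difference in slopes. The Protocol power table instead uses a "main effect for active treatment phase (assessed weekly, baseline-8weeks") for H1 and a "main effect for follow-up (assessed monthly, end of treatment-6 months") for H2. Baseline is therefore one of the nine H1 datapoints, while the H2 series leaves pre-treatment PDA out.

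**The concern.** The urn variables were chosen because they may predict outcome, and pre-treatment drinking is an obvious candidate predictor of later drinking. Both are known before treatment starts. A plan that does not say whether they enter the model leaves precision unused wherever they would reduce residual variance. It also leaves the choice of covariates open to being made after the equivalence check has been seen.

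With 90 participants and an effect of .35 as the criterion for a full trial (Protocol Section V.5, 1.d), the width of the interval matters. The question is how much is forgone, and for which of the two contrasts the documents name.

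**Working it through.** **Inputs.** From the Protocol power table: H1 effect .35, ICC .40, 9 datapoints, 45 per cell; H2 effect .50, ICC .80, 7 datapoints, 40 per cell; power .80 for both. Not in the documents, so assumed: alpha .05 (two-sided, with one-sided alongside), correlation r = .2/.3/.4 between pre-treatment PDA and each later value, outcome SD 1, complete data.

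**Step 1: the plan's own figure.** The variance of a participant mean over m points is (1+(m-1)ICC)/m.

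- H1: (1+8×.40)/9 = .467, giving power .784 one-sided and .681 two-sided.
- H2: (1+6×.80)/7 = .829, giving .792 one-sided and .690 two-sided.

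The stated .80 is approximately reproduced one-sided only, so both are shown below.

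**Step 2: average contrasts with pre-treatment PDA as covariate.** For H1, baseline moves from outcome to covariate, so the outcome is the mean of weeks 1-8: v = (1+7×.40)/8 = .475. The adjusted variance is v - r², SE = sqrt(2v/n), and two-sided power = Φ(effect/SE - 1.96).

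| | H1 v | H1 SE | H1 power, two-sided / one-sided | H2 v | H2 SE | H2 power, two-sided / one-sided |
|---|---|---|---|---|---|---|
| unadjusted | .475 | .1453 | .673 / .778 | .829 | .2035 | .690 / .792 |
| r = .2 | .435 | .1390 | .711 / .808 | .789 | .1986 | .712 / .809 |
| r = .3 | .385 | .1308 | .763 / .849 | .739 | .1922 | .740 / .831 |
| r = .4 | .315 | .1183 | .841 / .905 | .669 | .1828 | .781 / .862 |

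**Step 3: slope contrast.** In simulated random-intercept fits, adding a prognostic covariate as a main effect left the group-by-time SE at .0210 with and without it. A common baseline mean in both arms is a different device and does help. By generalised least squares (times 0-8, weekly correlation .40, baseline SD 1, 45 per arm), the slope variance falls from .000500/.000477/.000444 to .000381/.000363/.000331 for r = .2/.3/.4. The SE ratios are .873/.872/.863, a cut of 13-14%. The cut shrinks under other assumptions:

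- baseline SD .8: 8-10%;
- compound symmetry with ICC .50 or .60: 10% or 7%;
- random slopes with SD .10 or .15 per week at ICC .40: 7% or 4%.

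**Step 4: urn variables balanced but not modelled.** If they explain R² of the eight-week mean and are perfectly balanced, the actual two-sided size is 2(1-Φ(1.96/sqrt(1-R²))) = .039 at R² = .10 and .028 at R² = .20. This is the extreme case. A simulated urn (assumed settings: five balanced binary factors, one ball added per assignment, n = 90) left about 59% of the imbalance variance of simple randomisation, which gives roughly .045 and .041.

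**Step 5: the .35 criterion.** If it is read as a point estimate and the true effect is .46 (the low end quoted for the English-language trials), the chance of meeting it is Φ(.11/SE) = .775 unadjusted and .786/.800/.824 adjusted.

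**Step 6: cost of the covariates.** In 15,000 simulated trials, two-sided:

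- No covariate predicts PDA: H1 power falls from .669 to .643 (five covariates) or from .663 to .631 (six); H2 falls from .679 to .651 (five).
- r = .2 and uninformative urn variables: H1 goes from .664 to .679 (five) or from .662 to .665 (six).
- Urn variables explain a further 10%, five covariates, r = .2/.3/.4: H1 .729/.779/.868; H2 .725/.749/.797.

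**The case against.** Much of the opposing case stands.

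- A reader might infer that the plan rules out baseline adjustment or ignores baseline PDA. It does neither. Both covariate lists are open examples, the first describes earlier trials, and baseline is one of the nine H1 datapoints. The gap is one of specification.
- A reader might infer that precision is lost for the contrast the SAP calls its focus. It is not, as far as covariates go: main effects leave the slope SE unchanged when data are complete. The common baseline mean is a modelling choice, and its gain depends on the covariance structure.
- A reader might infer that the planned test is invalid. Leaving out balanced prognostic variables makes the average-contrast test at most mildly conservative, and the Protocol claims only a greater likelihood of balance.
- A reader might infer that the go/no-go decision is endangered. Read as a point estimate, the .35 criterion is met with almost the same probability either way.
- The gain depends on correlations the documents do not give. People who are physically dependent may be rescreened after detoxification, so a weak link between a short pre-treatment window and later PDA is plausible. Alcohol severity may also overlap with PDA.

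These points limit the claim. They do not remove it for the average contrasts or for H2, where the improvement uses data already held and the downside is small.

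**Conclusion.** The concern holds in a limited form. Neither document specifies adjustment for the urn variables or pre-treatment PDA, and H2 as laid out contains no pre-treatment drinking at all. For the average contrasts in the power table, adjusting for PDA would raise two-sided power by .04 to .17 for H1 (.67 to .71/.76/.84) and by .02 to .09 for H2 (.69 to .71/.74/.78). These figures come before the small loss for degrees of freedom and rest on the assumed alpha and correlations. If r is .2 and the urn variables predict nothing, H1 is close to break-even.

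The documents do not support a claim of inflated Type I error, of lost precision for the slope through missing covariates, or of a materially different chance of meeting the .35 criterion. The change should be made because it is cheap and better done before the data are seen.

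**What to change.** In SAP 1.c:

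1. For any average contrast on weeks 1-8 and for the H2 model, pre-specify as main-effect covariates pre-treatment PDA, gender, education, computer familiarity/access and acculturation, coded as in the urn. Include alcohol severity only if it is a different measure from baseline PDA.
2. State that the equivalence check in SAP 1.a does not alter this set.
3. Define the window for pre-treatment PDA. The Timeline Follow Back is already marked at screening.
4. Optionally, for the H1 slope, keep baseline PDA as the time-0 outcome with a common mean across arms, and give it its own variance and correlation or use robust standard errors. A plain random intercept with a common mean would have a Type I error of about .06-.08 if r is .2-.3 while the weekly ICC is .40. Do not apply the common mean to H2's first point, which is post-randomisation.

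Items 1-3 need SAP wording only and no new data; item 4 changes the fitted model. The covariate set uses 5-6 degrees of freedom and loses about .03 of power if none of the covariates predicts PDA.

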Human Investigation Committee Signature

This protocol is valid through

SECTION V: RESEARCH PLAN**1. Statement of Purpose:** State the scientific aim(s) of the study, or the hypotheses to be tested.

The goal of this project is to address a major challenge in health disparities as defined by NIH and the Institute of Medicine, specifically, the need for accessible, effective, evidence-based treatments for Latino/as.

Specific aims are as follows:

- To adapt our existing CBT4CBT program for use with Spanish-speaking alcohol users in a web-based platform
- To conduct an 8-week randomized trial evaluating the feasibility and efficacy of adding CBT4CBT-Spanish to treatment as usual in a community based treatment program in a population of 90 Spanish-speaking individuals who meet current criteria for alcohol use disorder
- To evaluate the long-term durability and/or delayed emergence of treatment effects through a six month follow-up after termination of the study treatments. Given previous evidence regarding the durability of standard clinician-delivered CBT₄₁ and computer-assisted CBT4CBT₂₅, we hypothesize that CBT4CBTSpanish will be significantly more effective than standard treatment alone through the follow-up.

2. Background: Describe the background information that led to the plan for this project.

Provide references to support the expectation of obtaining useful scientific data.

A Health disparities among Latinos, accessibility of evidence based therapies (EBTs).

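### The sample-size text claims an effect of .35 is detectable for both hypotheses, but the plan's own power table supports .35 only for H1 and gives .50 for H2

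*Protocol*

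**What the plan says.** Protocol Section V, item 5, part 1.d states that "the proposed sample sizes will enable us to detect effect sizes of .35 or higher for either hypothesis, which will be the criterion", and the sentence goes on: "for determining whether CBT4CBT-Spanish-Alcohol has adequate promise to justify a fully powered randomized trial". It names the sample-size software but gives no alpha and does not say whether the test is one- or two-sided.

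The power table that follows has two rows:

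| Row | Power | Effect size | ICC | Datapoints | n per cell |
|---|---|---|---|---|---|
| H1, "main effect for active treatment phase (assessed weekly, baseline-8weeks" | .80 | .35 | .40 | 9 | 45 |
| H2, "main effect for follow-up (assessed monthly, end of treatment-6 months" | .80 | .50 | .80 | 7 | 40 |

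Three other statements bear on this:

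- The third aim in Section V, item 1 hypothesises that the program "will be significantly more effective than standard treatment alone through the follow-up".
- Part 1.c expects that "we estimate that our extensive efforts to track participants will yield a 90% follow-up rate".
- Part 1.c also puts the focus of the repeated-measures analysis on the contrast-by-time effect, "which essentially evaluates whether the slopes, or rates of change, of one group differ from the slopes of another group".

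The available SAP text covers outcomes, attrition and modelling. It has no sample-size section, so it does not settle the matter.

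**The concern.** The sentence and the table cannot both describe H2. The table is the only support offered for the sentence, and it gives .80 power at .35 for H1 alone. No power figure is given anywhere for H2 at .35.

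This matters because durability is a specific aim with a stated hypothesis of a significant difference, and because the same sentence sets the threshold for moving to a full trial. A reader who takes .35 as equally detectable in both phases could read a non-significant follow-up result as evidence against an effect of that size. On the table's own figures, the design would miss a true .35 at follow-up roughly half the time.

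**Working it through.** **Inputs.** All come from the power table and part 1.c: H1 (effect .35, ICC .40, m = 9, n = 45 per cell); H2 (effect .50, ICC .80, m = 7, n = 40 per cell); follow-up rate 90%. Alpha is not stated. I assume 5% and show both one- and two-sided results.

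**Step 1: reproduce the table.** The documents give no formula. I assume a time-averaged difference under compound symmetry, with SE = sqrt(2[1 + (m−1)ICC]/(m·n)) and power = Φ(effect/SE − z_crit).

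- H1: SE = sqrt(2 × 4.2/(9 × 45)) = .1440; .35/.1440 = 2.430. Power is .78 one-sided and .68 two-sided.
- H2: SE = sqrt(2 × 5.8/(7 × 40)) = .2035; .50/.2035 = 2.457. Power is .79 one-sided and .69 two-sided.

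The table's .80 is therefore approached by a one-sided 5% test and not by a two-sided one. The H2 cell size fits the expected retention: .90 × 45 = 40.5.

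**Step 2: H2 at .35, taking the row at face value.** This step does not need the formula above. It accepts .80 power at .50 with 40 per cell, and uses the fact that the expected z is proportional to the effect and to sqrt(n). At .50 the expected z is z_crit + .8416, and .35/.50 = .70.

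- Two-sided: .70 × (1.960 + .8416) = 1.961; power = Φ(1.961 − 1.960) = .50.
- One-sided: .70 × (1.645 + .8416) = 1.741; power = Φ(1.741 − 1.645) = .54.

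**Step 3: no loss to follow-up.** With 45 per cell, multiply z by sqrt(45/40) = 1.0607.

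- Two-sided: 2.080, power .55.
- One-sided: 1.846, power .58.
- Effect with .80 power: .50 × sqrt(40/45) = .47.

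**Step 4: cell size for .80 power at .35.** On the row at face value, 40 × (.50/.35)² = 81.6, so 82 per cell (164 in total), against 90 randomized.

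**Step 5: cross-check with the Step 1 formula.** At .35 and 40 per cell, .35/.2035 = 1.720, giving power .53 one-sided and .41 two-sided. At 45 per cell it gives .57 and .45. The effect with .80 power at 40 per cell is .51 one-sided and .57 two-sided. The cell size needed for .80 power at .35 is 84 one-sided and 107 two-sided.

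| H2 power at .35 | One-sided 5% | Two-sided 5% |
|---|---|---|
| Row at face value, n = 40 | .54 | .50 |
| Row at face value, n = 45 | .58 | .55 |
| Assumed formula, n = 40 | .53 | .41 |
| Assumed formula, n = 45 | .57 | .45 |

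**Step 6: could another model make .35 detectable for H2?** Two were tried. Adjusting for the first of the seven datapoints gives two-sided power of about .95 at .35. A slope contrast reaching a difference of .35 at the last point gives about .87. But for an effect of .50 these models need only about 13 and 17 per cell for .80 power. They do not reproduce the row's 40 per cell, and the row is labelled a main effect.

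**The case against.** **The table already prints .50, and this is a pilot.** Both are true, and they limit the consequences. They do not make the sentence right: it carries the criterion, and it contradicts the row below it.

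**The criterion may mean an observed effect of at least .35.** The wording allows that reading, and a threshold on the estimate would need neither significance nor .80 power. The rule itself would then survive. The separate claim that .35 is detectable under both hypotheses would still conflict with the H2 row.

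**The effects the plan cites are larger.** Part 1.d reports .46 to .59 from the earlier English-language trials. Scaling the H2 row as in Step 2, power at 40 per cell over that range is about .73 to .91 two-sided (.74 to .90 one-sided). So .50 is a defensible planning value for H2, and the follow-up comparison is not weak at the effects the plan cites. This supports the table, not the sentence.

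**The two-sided figures are fragile.** They accept the row's .80, although the assumed formula gives only .69 two-sided at .50. This stands as a caution: 82 per cell is conditional on the row, and the formula gives 84 to 107. The one-sided figures agree closely across the two routes (.54 and .53), and every route that fits the row is far below .80.

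**Slope contrast and table label.** Both rows already say main effect, so the label is not missing. What the text lacks is a statement that this power does not refer to the slope contrast named as the focus in part 1.c. That is a secondary point.

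**Conclusion.** The concern holds. The statement that .35 is detectable applies to H1 only. On the plan's own H2 row, power at .35 is .50 to .54 with the planned 40 per cell and .55 to .58 with full retention. The effect detectable with .80 power is .50, or .47 with no loss. These figures rest on a 5% test, a normal approximation and the H2 row being correct. If the row is instead recomputed under the assumed compound-symmetry formula, power at .35 with 40 per cell is .53 one-sided or .41 two-sided, so the conclusion does not depend on the missing alpha. This is a text-to-table inconsistency attached to a decision criterion. It should be fixed, but it does not call for a larger trial.

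**What to change.** In Protocol Section V, item 5, part 1.d:

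1. Limit the .35 statement to H1, and give .50 as the effect detectable with .80 power for H2, as in the table.
2. Say what the .35 criterion applies to: either that it rests on H1, or what figure holds for H2. Also say whether it refers to the observed effect or to a significant result. This choice belongs to the investigators; the documents do not settle it.
3. State the alpha and sidedness behind the .80 and recheck both rows against them. If the intended test is two-sided 5%, the assumed formula gives .68 and .69 rather than .80.
4. Add one line saying that the table gives power for the main effect, not for the contrast-by-time effect in part 1.c.

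The cost is a protocol text change, a short recalculation and one decision on the criterion. No patients are added and no endpoint or analysis changes. The stated H2 detectable effect becomes less favourable (.50 instead of .35).

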In years 3-5 of the proposed project, we will conduct a Stage 1 randomized clinical trial evaluating the program in which 90 Spanish-speaking individuals with alcohol use disorder will be randomized to (1) standard outpatient counseling at the Hispanic Clinic (ST; typically consisting of weekly individual and group supportive counseling) or (2) CBT4CBT-Spanish as an adjunct to ST. Other aspects of the trial will parallel those in our completed trial of the English version of CBT4CBT-Alcohol¹⁶ to facilitate comparability across studies. Treatments will be delivered over an 8-week period with a 6-month follow-up to assess durability and/or delayed emergence of treatment effects. The primary outcome measure will be percent days of

abstinence (PDA) by week. Secondary outcomes include percent heavy drinking days and number of individuals with no heavy drinking days in the last 4 weeks of treatment¹⁹.

2. Participants

Participants will be 90 individuals seeking treatment for alcohol use at the Hispanic Clinic of CMHC. The clinic treats a heterogeneous population, where 42% of those in the co-occurring treatment program report alcohol as their principal substance related issue and 43% are women. As reported above, we have demonstrated our ability to recruit, randomize, retain, and follow-up high numbers of closely related samples in this setting^{191, 192}.

a. Inclusion and exclusion criteria

Participants will be included who are (1) 18 years of age or older, (2) applying/referred for outpatient alcohol treatment, (3) meet current DSM-IV/DSM-5 criteria for alcohol use disorder with use in the past 30 days, (4) speak Spanish as their preferred or principal (most commonly spoken) language, (5) sufficiently stable for 8 weeks of outpatient treatment, and (6) willing to provide locator information and be contacted for follow-up for 6 months. Individuals will be excluded who (1) have an untreated/unstable bipolar or schizophrenic disorder, or (2) have a current legal case pending such that incarceration during the 8-week protocol is likely. Those physically dependent on alcohol can be rescreened following detoxification/stabilization (see Human Subjects).

b. Rationale for sample choice (also see Human Subjects section).

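### The .35 go criterion is not tied to a defined rule, and the tabulated .80 power is not the chance of meeting it: on the observed-effect reading a true .35 passes 50% of the time per hypothesis

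*Protocol*

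**What the plan says.** The Adequacy of sample size paragraph (Protocol Section V, item 5, 1.d) says that the trial can "detect effect sizes of .35 or higher for either hypothesis, which will be the criterion for determining whether CBT4CBT-Spanish-Alcohol has adequate promise". The decision at stake is whether a larger, fully powered trial is warranted. The next sentence sets this beside the effect sizes that the English-language trials yielded, .46 to .59.

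The table that follows is headed "Power calculations for random effects regression". Each row gives power, effect size, ICC, number of datapoints and sample size per cell:

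- H1, a main effect over the treatment phase: "assessed weekly, baseline-8weeks) .80 .35 .40 9 45".
- H2, a main effect over follow-up: "assessed monthly, end of treatment-6 months) .80 .50 .80 7 40".

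Neither the paragraph nor the table gives an alpha or says whether the test is one-sided or two-sided. They also do not say whether the criterion applies to the point estimate or to the test, or whether it must be met on one hypothesis or on both. The SAP text available repeats the analysis strategy but has no sample-size paragraph and no go criterion, so it does not settle the question.

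**The concern.** Power of .80 at .35 is the chance that a test of no difference is significant when the true effect is .35. It is not the chance that the trial shows an effect of .35 or more. Using .35 as both the design effect and the criterion invites the reader to carry the .80 over to the go decision.

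The wording also extends .35 to both hypotheses, although the H2 row was sized for .50.

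The practical risk is a decision that can be read two ways once the data are in. An observed H1 effect of .30 would be significant at .05 (the boundary is about .24 one-sided, .28 two-sided) but below .35. An observed H2 effect of .37 would be above .35 but not significant two-sided (boundary about .40). Whether either result shows adequate promise depends on a rule that is not written down.

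**Working it through.** **Inputs** (Protocol Section V, item 5, 1.d, table). H1: n = 45 per cell, k = 9 datapoints, ICC = .40, design effect .35. H2: n = 40, k = 7, ICC = .80, design effect .50. The 45 per cell agrees with 90 randomized to two arms, and the 40 is close to 45 × .90 = 40.5 from the expected 90% follow-up.

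**Assumptions.** Equal correlation between all assessments; effects in units of the single-assessment SD; alpha .05, with both sidednesses shown.

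**Standard error of the standardised main effect:** SE = √[(2/n) × (1 + (k − 1) × ICC)/k]

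- H1: √[(2/45) × (1 + 8 × .40)/9] = .144
- H2: √[(2/40) × (1 + 6 × .80)/7] = .2035

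**Step 1. The plan's own figure.** Power = Φ(effect/SE − z), with z = 1.645 one-sided or 1.960 two-sided.

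- H1 at .35: .784 one-sided, .681 two-sided
- H2 at .50: .792 one-sided, .690 two-sided

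The tabulated .80 is therefore reproduced, to within two percentage points, only as the power of a one-sided .05 significance test.

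**Step 2. H2 at .35 instead of .50.** .35/.2035 = 1.720, which gives .53 one-sided and .41 two-sided. The claim that .35 is detectable on either hypothesis does not agree with the H2 row.

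**Step 3. Criterion applied to the observed effect.** P(estimate ≥ .35) = 1 − Φ((.35 − true effect)/SE).

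| True effect | H1 | H2 |
|---|---|---|
| 0 | .008 | .043 |
| .35 | .50 | .50 |
| .46 | .78 | .71 |
| .59 | .95 | .88 |

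The .50 depends on neither alpha, ICC nor n. It holds for any unbiased estimator with a symmetric distribution when the cut-off equals the true effect.

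**Step 4. True effect needed for an 80% chance of passing:** .35 + .8416 × SE.

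- H1: .35 + .8416 × .144 = .471
- H2: .35 + .8416 × .2035 = .521

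**Step 5. Two hypotheses together, both true effects .35.** With correlation ρ between the two estimates, P(both pass) = 1/4 + arcsin(ρ)/(2π), and P(at least one passes) = 1 − P(both pass).

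- ρ = 0: both .25, at least one .75
- ρ = .9: both .43, at least one .57

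**Step 6. Criterion read as significance.** At a true .35 the pass chance is .78 (one-sided) or .68 (two-sided) for H1 from Step 1, and .53 or .41 for H2 from Step 2. The smallest significant observed effects are z × SE: .237 or .282 for H1, and .335 or .399 for H2.

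**The case against.** The best defence is that the paragraph never mentions a point estimate. Beside a power table, to detect an effect ordinarily means to obtain a significant result, and on that reading the H1 figure is .78 or .68, not .50. This stands: the observed-effect reading is the more natural one, because the next sentence compares .35 with effects that earlier trials yielded, but the text does not settle it. It does not rescue the paragraph, because the significance reading fails for H2 at .35.

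A demanding observed-effect bar is also a legitimate choice for a Stage 1 trial. On H1 it passes 0.8% of the time at no effect, 78% at .46 and 95% at .59. So nothing here shows that .35 is the wrong bar or that a significance rule should replace it.

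Three stronger inferences are tempting and not supported:

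- That the plan promises an 80% chance of a go and delivers 50%. The plan states no go probability, and its .80 at .35 is for H1 only.
- That 50% is the pass rate of the whole rule. It is the rate for one hypothesis. If meeting the criterion on either is enough, it is about 57% to 75%; if both are required, about 25% to 43%.
- That significant H1 results below .35 would fail the criterion. If the criterion is significance, they pass; they fail only if it is the observed effect. The two readings cannot be combined.

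One further limit: the table is for main effects, whereas the analysis sections of the Protocol and SAP focus on differences in slope. If the criterion were read from a slope contrast, the .47 and .52 would have to be recalculated. The 50% at a true effect equal to the cut-off would not change.

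**Conclusion.** The concern holds as a matter of definition and reporting. The go criterion is not specified, and under neither reading does it have the tabulated .80 at .35 for both hypotheses: the pass chance is .50 and .50 on the observed effect, and .78/.68 (H1) and .53/.41 (H2) on a one-/two-sided test. The conflict between .35 for both hypotheses and the H2 row's .50 needs no interpretation. The .50 rests only on a symmetric, unbiased estimate. The other single-hypothesis figures rest on equal correlation and single-assessment SD units, and those for significance also on an alpha of .05 that the documents do not state. The combined figures assume jointly normal estimates with correlation from 0 to .9.

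**What to change.** In Protocol Section V, item 5, 1.d:

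1. Replace the claim that .35 is detectable on both hypotheses: .35 is the design effect for H1 and .50 for H2.
2. Say that .80 is the power of the significance test at those effects and not the chance of meeting the .35 criterion, and give the alpha and sidedness used.
3. Keep the criterion that the sponsor prefers, but state whether it applies to the estimate or to the test, on H1, H2, either or both, and give its pass probabilities. If an observed .35 is kept, these are, per hypothesis, .50 at a true effect of .35, and .80 only at about .47 (H1) or .52 (H2).

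The same sentences should go into the SAP if it is to govern the decision. The cost is a few sentences and a less favourable stated figure. Sample size, visits and data collection do not change.
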